Appendix C Elements of the Subject Informed Consent

In seeking informed consent, the following information shall be provided to each subject:

1. A statement that the study involves research.
2. An explanation of the purposes of the research.
3. The expected duration of the subject's participation.
4. A description of the procedures to be followed, including invasive procedures.
5. The identification of any procedures that are experimental.
6. The estimated number of subjects involved in the study.
7. A description of the subject's responsibilities.
8. A description of the conduct of the study.
9. A statement describing the treatment(s) and the probability for random assignment to each treatment.
10. A description of the possible side effects of the treatment that the subject may receive.
11. A description of any reasonably foreseeable risks or discomforts to the subject and, when applicable, to an embryo, fetus, or nursing infant.
12. A description of any benefits to the subject or to others that reasonably may be expected from the research. When there is no intended clinical benefit to the subject, the subject should be made aware of this.
13. Disclosures of appropriate alternative procedures or courses of treatment, if any, that might be advantageous to the subject and their important potential risks and benefits.
14. A statement describing the extent to which confidentiality of records identifying the subject will be maintained, and a note of the possibility that regulatory agencies, auditor(s), IRB/IEC, and the monitor may inspect the records. By signing a written informed consent form, the subject or the subject's legally acceptable representative is authorizing such access.
15. For research involving more than minimal risk, an explanation as to whether any compensation and an explanation as to whether any medical treatments are available if injury occurs and, if so, what they consist of or where further information may be obtained.
16. The anticipated prorated payment(s), if any, to the subject for participating in the study.
17. The anticipated expenses, if any, to the subject for participating in the study.
18. An explanation of whom to contact for answers to pertinent questions about the research (investigator), subject's rights, and IRB/IEC and whom to contact in the event of a research-related injury to the subject.

19. A statement that participation is voluntary, that refusal to participate will involve no penalty or loss of benefits to which the subject otherwise is entitled, and that the subject may discontinue participation at any time without penalty or loss of benefits to which the subject is otherwise entitled.
20. The consequences of a subject's decision to withdraw from the research and procedures for orderly termination of participation by the subject.
21. A statement that the subject or the subject's legally acceptable representative will be informed in a timely manner if information becomes available that may be relevant to the subject's willingness to continue participation in the study.
22. A statement that results of pharmacogenomic analysis will not be disclosed to an individual, unless prevailing laws require the sponsor to do so.
23. The foreseeable circumstances or reasons under which the subject's participation in the study may be terminated.
24. A written subject authorization (either contained within the informed consent form or provided as a separate document) describing to the subject the contemplated and permissible uses and disclosures of the subject's personal information (including personal health information) for purposes of conducting the study. The subject authorization must contain the following statements regarding the uses and disclosures of the subject's personal information:
 - a) That personal information (including personal health information) may be processed by or transferred to other parties in other countries for clinical research and safety reporting purposes, including, without limitation, to the following: (1) Takeda, its affiliates, and licensing partners; (2) business partners assisting Takeda, its affiliates, and licensing partners; (3) regulatory agencies and other health authorities; and (4) IRBs/IECs;
 - b) It is possible that personal information (including personal health information) may be processed and transferred to countries that do not have data protection laws that offer subjects the same level of protection as the data protection laws within this country; however, Takeda will make every effort to keep your personal information confidential, and your name will not be disclosed outside the clinic unless required by law;
 - c) That personal information (including personal health information) may be added to Takeda's research databases for purposes of developing a better understanding of the safety and effectiveness of the study medication(s), studying other therapies for patients, developing a better understanding of disease, and improving the efficiency of future clinical studies;
 - d) That subjects agree not to restrict the use and disclosure of their personal information (including personal health information) upon withdrawal from the study to the extent that the restricted use or disclosure of such information may impact the scientific integrity of the research; and

- e) That the subject's identity will remain confidential in the event that study results are published.
- 25. Female subjects of childbearing potential (eg, non-sterilized, premenopausal female subjects) who are sexually active must use adequate contraception (as defined in the informed consent) from Screening throughout the duration of the study. Regular pregnancy tests will be performed throughout the study for all female subjects of childbearing potential. If a subject is found to be pregnant during study, study medication will be discontinued and the investigator will offer the subject the choice to receive unblinded treatment information.
- 26. A statement that clinical trial information from this trial will be publicly disclosed in a publicly accessible website, such as ClinicalTrials.gov.

Appendix D Investigator Consent to Use of Personal Information

Takeda will collect and retain personal information of investigator, including his or her name, address, and other personally identifiable information. In addition, investigator's personal information may be transferred to other parties located in countries throughout the world (eg, the United Kingdom, United States, and Japan), including the following:

- Takeda, its affiliates, and licensing partners.
- Business partners assisting Takeda, its affiliates, and licensing partners.
- Regulatory agencies and other health authorities.
- IRBs and IECs.

Investigator's personal information may be retained, processed, and transferred by Takeda and these other parties for research purposes including the following:

- Assessment of the suitability of investigator for the study and/or other clinical studies.
- Management, monitoring, inspection, and audit of the study.
- Analysis, review, and verification of the study results.
- Safety reporting and pharmacovigilance relating to the study.
- Preparation and submission of regulatory filings, correspondence, and communications to regulatory agencies relating to the study.
- Preparation and submission of regulatory filings, correspondence, and communications to regulatory agencies relating to other medications used in other clinical studies that may contain the same chemical compound present in the study medication.
- Inspections and investigations by regulatory authorities relating to the study.
- Self-inspection and internal audit within Takeda, its affiliates, and licensing partners.
- Archiving and audit of study records.
- Posting investigator site contact information, study details and results on publicly accessible clinical trial registries, databases, and websites.

Investigator's personal information may be transferred to other countries that do not have data protection laws that offer the same level of protection as data protection laws in investigator's own country.

Investigator acknowledges and consents to the use of his or her personal information by Takeda and other parties for the purposes described above.

Appendix E Sample of Subject Diary and The Bristol Stool Scale

This table provides a sample of the subject diary, which will be provided to subjects on Day -15 of the Screening Visit and in which they are to record every defecation event from Day -15 until Day 29. The diary prompts the subject to record all details of each event including the consistency of the stool and the difficulty they have in passing it. The second page of the appendix is the Bristol Stool Scale, which will be supplied to the subjects as an aid.

A. Date and time they take the study drug

B. After a bowel movement:

a. Date and time

b. Stool consistency

1 = Hard and round (difficult-to-pass) stool like those of rabbits

2 = Sausage-shaped but hard stool

3 = Sausage-shaped stool with cracks on the surface

4 = Sausage-shaped, soft stool with smooth surface, or coiled stool (like a snake)

5 = Soft, half-solid (and easy-to-pass) stool with clear crease

6 = Unshaped, loose stool with small, irregular-shaped pieces, or mushy stool

7 = Watery stool without solid pieces (entirely liquid)

c. Degree of straining:

0 = No straining

1 = Mild straining

2 = Moderate straining

3 = Strong straining

4 = Very strong straining

d. CCI

CCI

CCI

C. Abdominal symptom (bloating and discomfort)

Abdominal bloating:

0 = None (no abdominal distention)

1 = Mild (Slight abdominal distention)

2 = Moderate (Abdominal distention clearly felt)

3 = Severe (Severe abdominal distension)

4 = Very severe (Extremely strong abdominal distension)

Abdominal discomfort:

0 = None (no abdominal discomfort)

1 = Mild (Slight abdominal discomfort)

2 = Moderate (Abdominal discomfort clearly felt)

3 = Severe (Abdominal discomfort with pain)

4 = Very severe (Abdominal discomfort with severe pain)

D. Date and time a rescue medication was used (if applicable)

E. Concomitant drugs (if applicable)

The investigator or clinical research coordinator will instruct the subjects to keep the diary throughout the study. If the investigator or coordinator asks a subject about diary entries and adds a note or corrects the diary for clarification, each note/correction will be marked with the date and signature and the reason for the correction. The investigator will maintain the diaries as part of the subject's file at the site.

Bristol Stool Chart

Type 1		Separate hard lumps, like nuts (hard to pass)
Type 2		Sausage-shaped but lumpy
Type 3		Like a sausage but with cracks on its surface

3.0 LIST OF ABBREVIATIONS

AE	adverse event
ALT	alanine aminotransferase
ANCOVA	analysis of covariance
ANOVA	analysis of variance
AST	aspartate aminotransferase
BID	bis in die (twice a day)
BM	bowel movement
BMI	body mass index
BUN	blood urea nitrogen
CIC	chronic idiopathic constipation
CPK	creatine phosphokinase
CRF	case report form
ECG	electrocardiogram
FAS	full analysis set
GGT	γ -glutamyl transferase
HIV	human immunodeficiency virus
ICH	International Conference on Harmonisation
IVRS	Interactive Voice Response System
LDH	lactate dehydrogenase
LLN	lower limit of normal
LOCF	last observation carried forward
MedDRA	Medical Dictionary for Regulatory Activities
mg	milligram
PAC-QoL	patient assessment of constipation – quality of life
PD	pharmacodynamics
PK	pharmacokinetics
QOL	quality-of-life
PPS	per protocol set
PRO	patient-reported outcome
SAE	serious adverse event
SAF	safety analysis set
SAP	statistical analysis plan
SBM	spontaneous bowel movement
SD	standard deviation
SDB	standard database
TLGs	tables, listings, and graphs
ULN	upper limit of normal
WHODrug	World Health Organization Drug Dictionary

Printed or downloaded documents must be verified against the effective version.

CONFIDENTIAL INFORMATION

Do not distribute outside of Takeda without a confidentiality agreement.

CROSS-REGIONAL TEMPLATE

Template Number: C-TMPL-DO-801

Page: 5 of 28

Version Number: 1.2

Effective Date: 14 Sep 2015

This version replaces: 1.1

Parent Document: C-SOP-DO-800

Template Title: Statistical Analysis Plan (Legacy Takeda)

4.0 OBJECTIVES

4.1. PRIMARY OBJECTIVES

The primary objective of this study is to evaluate the efficacy and safety of oral administration of lubiprostone 24 µg BID for 4 weeks in subjects with CIC compared with placebo.

4.2. STUDY DESIGN

This is a phase 3, randomized, double-blind, parallel-group, placebo-controlled study in subjects with CIC as determined by the Rome III Diagnostic Criteria for Functional Constipation [4].

This study consists of a 14-day Screening Period and a subsequent 4-week (28 days) Double-Blind Treatment Period in which subjects will receive either lubiprostone or matching placebo twice a day. Subjects will be randomized to either active lubiprostone or placebo in a 1:1 ratio.

During the Screening Period, the defecation behavior of each subject is recorded in a diary to confirm he/she has constipation. Use of all existing laxatives is stopped at the beginning of the Screening Period (Visit 1). Subjects are instructed not to change their diet or lifestyle habits during the study. A total of 10 mg of bisacodyl suppository (or any equivalent drug) may be prescribed as a standard rescue medication if a subject has no adequate bowel movement for 3 consecutive days during the Screening Period of the study. When bisacodyl suppository does not improve constipation, glycerin enema (or equivalent drug) will be given. Subjects are instructed to complete their diaries before using rescue medications.

The subject diary will be distributed on Study Days -15, -1, 8 and 15. Subjects will be instructed to keep the diary every day including on the morning of Visit 1.

If the rescue medications fail to improve constipation, the investigator may decide to use another rescue medication. The recommendation may include a medication from the excluded medication list other than any form of polyethylene glycol (PEG), linaclotide, methylnaltrexone, or prucalopride, all of which are considered prohibited rescue medications. No rescue medication may be given 24 hours prior to and until 48 hours after the first dose of the study drug (Day 1). Subjects who use a rescue medication within 24 hours before the first dose of study drug on Day 1 should be withdrawn from the study. Those who use a rescue medication within 48 hours after dosing on Day 1 will be discontinued from the study by the investigator. The dose and mode of administration of rescue medications must be recorded in the electronic case report form (eCRF).

Approximately 204 subjects whose constipation is confirmed during the Screening Period will be randomized in the Double-Blind Treatment Period to receive either lubiprostone or matching placebo BID. Others whose constipation does not satisfy the criteria during the 14-day Screening Period or those who receive a rescue medication within 24 hours prior to the first dose on Day 1 are ineligible for randomization in the Double-Blind Treatment Period and therefore will be excluded from the study. Subjects who satisfy the inclusion criteria and do not meet the exclusion criteria are randomized to 1 of the treatment groups in the order of the number

CROSS-REGIONAL TEMPLATE

Template Number: C-TMPL-DO-801

Page: 6 of 28

Version Number: 1.2

Effective Date: 14 Sep 2015

This version replaces: 1.1

Parent Document: C-SOP-DO-800

Template Title: Statistical Analysis Plan (Legacy Takeda)

assigned. Approximately 204 subjects with CIC will be randomized to 2 groups: active treatment or placebo in a 1:1 ratio (102 subjects each) in a double-blinded manner.

[figure not shown]
Subjects are to begin their study drug treatment twice daily (after breakfast and dinner) in the morning following Visit 2.

Subjects will return to the study site on approximately Study Days 8, 15, and 29 during the 4 weeks of double-blind treatment and will be followed for an additional 2 weeks during the Follow-Up Period, in which no treatment will be administered.

At the investigator's discretion, with consideration given to subjects' bowel movement frequency and consistency, dose adjustments (dose reduction) may be made in a double-blind manner. Dose adjustment should be documented in the subject's source notes. Procedure for reduction of study drug dose due to Adverse Events is described in Section [7.7](#).

Subjects who withdraw prematurely will be seen within 1 week of discontinuation for an Early Termination Visit. A schematic of the study design is included as [Figure 1](#). A schedule of assessments is listed in Appendix A

Figure 1 Schematic of Study Design

CROSS-REGIONAL TEMPLATE

Template Number: C-TMPL-DO-801

Page: 7 of 28

Version Number: 1.2

Effective Date: 14 Sep 2015

This version replaces: 1.1

Parent Document: C-SOP-DO-800

Template Title: Statistical Analysis Plan (Legacy Takeda)

5.0 ANALYSIS ENDPOINTS

Primary Endpoint

Spontaneous bowel movement (SBM) frequency in Week 1 of study drug administration.

Secondary Endpoints

SBM frequency (Week 2, 3, and 4).

Proportion of subjects who have a SBM within 24 hours after first dose.

Mean degree of straining (Week 1, 2, 3, and 4).

Mean degree of stool consistency (Week 1, 2, 3, and 4).

Weekly abdominal symptoms score (bloating and discomfort) (Week 1, 2, 3, and 4).

Additional Endpoints

Quality of life evaluation using the standard Patient Assessment of Constipation—Quality of Life (PAC-QOL) Questionnaire.

Safety

The safety of lubiprostone will be evaluated by the following parameters:

Adverse events (AEs)

Clinical laboratory values.

Vital signs, including body temperature, blood pressure, heart rate, and body weight.

Physical examination.

Exploratory Endpoints

CCI

CROSS-REGIONAL TEMPLATE

Template Number: C-TMPL-DO-801 **Page:** 8 of 28
Version Number: 1.2 **Effective Date:** 14 Sep 2015
This version replaces: 1.1
Parent Document: C-SOP-DO-800
Template Title: Statistical Analysis Plan (Legacy Takeda)

6.0 DETERMINATION OF SAMPLE SIZE

Assuming equal allocation, a power of 90%, an alpha level of 0.05 for a 2-sided test, a placebo mean of 4, a treatment mean of 5.9 and a common standard deviation of 4 for SBM frequency at Week 1 and using the Wilcoxon-Mann-Whitney test [1], a total sample size of 198 is required. The Wilcoxon-Mann-Whitney test is a non-parametric test of the null hypothesis that the distribution is the same for both placebo and treatment responses against the alternative that there is a location difference between the two. The primary analysis will be conducted using the van Elteren test, which is a stratified version of the Wilcoxon-Mann-Whitney test; use of the Wilcoxon-Mann-Whitney test for sample size estimation will provide an approximate sample size for the van Elteren analysis. The estimates of placebo and treatment response are based on a previous study conducted by Sucampo Pharmaceuticals in the United States of America (Protocol No. SPI/0211SC0232).

The primary endpoint requires subjects to complete at least 4 days of the study diary, therefore assuming a non-evaluable rate of 3% by Day 4 an additional 6 subjects are required, giving a total of 204 subjects.

CROSS-REGIONAL TEMPLATE

Template Number:	C-TMPL-DO-801	Page:	9 of 28
Version Number:	1.2	Effective Date:	14 Sep 2015
This version replaces:	1.1		
Parent Document:	C-SOP-DO-800		
Template Title:	Statistical Analysis Plan (Legacy Takeda)		

7.0 METHODS OF ANALYSIS AND PRESENTATION

7.1 GENERAL PRINCIPLES [OR CONSIDERATIONS]

Continuous data will be summarized using number of subjects (N), mean, standard deviation (SD), median, minimum, and maximum. Summary statistics for continuous data will only include subjects with a non-missing value for the data being summarized.

Categorical data will be summarized using the number and percent of subjects for each category where appropriate. Missing categories will be used for categorical data when missing data is present. The calculation of percentages will take into account missing responses.

All confidence intervals, statistical tests, and resulting p-values will be reported as 2-sided unless otherwise stated. P-values (when rounded to three decimals) less than or equal to α ($=0.05$) are reported as “statistically significant”.

Means, LS means, and medians will be presented to 1 more decimal place than the recorded data. Where presented, SDs and standard errors will be presented to 2 more decimal places than the recorded data. Confidence intervals for parameter estimates will be presented using the same number of decimal places as those recorded for the parameter point estimate.

Alternative methods of analysis of the data may be considered prior to un-blinding should some of the assumptions underlying the proposed analyses not be met. However, the reasons for any departures from the planned approach and methods will be documented fully.

Centers may be pooled geographically if necessary for analysis purposes.

Version 9.4 or later of SAS®, will be used to provide all data summaries, statistical analyses, and data listings.

CROSS-REGIONAL TEMPLATE

Template Number: C-TMPL-DO-801

Page: 10 of 28

Version Number: 1.2

Effective Date: 14 Sep 2015

This version replaces: 1.1

Parent Document: C-SOP-DO-800

Template Title: Statistical Analysis Plan (Legacy Takeda)

Study Visit Windows

For BM data the assignment of data to each week (1, 2, 3 and 4) will be calculated from the date and time of the morning dose on Day 1. If no morning dose was taken on Day 1, then the date of Day 1 will be used and the time of the first recorded morning dose will be used. Weeks will be calculated as 168-hour intervals starting from this time. Note that any diary entries prior to this will be assigned to the screening period. Where missing dates or times do not allow the assignment of diary data to a treatment period (Screening or double blind) then it will be assumed that all data in the Screening booklet was recorded during Screening and all data in the remaining booklets were recorded after the booklets were provided to subjects. Abdominal symptom assessments will be assigned to the week as recorded in the diary. PAC-QOL is assessed at Day -1, Week 2 (Day 15) and Week 4 (Day 29). PAC-QOL assessments will be assigned to the time point relating to the visit at which they are recorded, regardless of actual study day. Assessments conducted at an Early Termination Visit will be assigned to the next scheduled visit that would have taken place if the subject had not discontinued, e.g. if the subject withdraws prior to Week 2 then the Early Termination Visit assessment will map to Week 2, whereas if the Early Termination Visit occurs after Week 2 then the assessment will be assigned to Week 4. Study visits are presented in the table below.

Study Day/Week	Screening		Double Blind Treatment Period				Follow-up Phone Contact
	Screening	Randomization	First Dose	Week 1	Week 2	Final Visit / Early Termination Visit Week 4	
Visit Number:	1	2	-	3	4	5	-
Day	-15	-1	1	8	15	29	43

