7.8 EFFICACY ANALYSIS

The primary and secondary endpoints will be derived from the daily diary data entered by patients.

Two-sided tests at a significance level of $\alpha=5\%$ will be used throughout unless otherwise stated. The null hypothesis is that lubiprostone is equal to placebo against the alternative that lubiprostone is different to placebo. All analyses will be performed using the FAS. Analyses specified for the PP are to be regarded as supportive evidence. There will be no adjustment for multiplicity.

All efficacy endpoints will be summarized by treatment and visit. If baseline measures are also defined and collected for an efficacy endpoint then change from Baseline at each visit will also be presented by summary statistics by treatment and visit. Change from baseline will be calculated as (post-baseline value) – (baseline value). Baseline is defined as the last recorded measurement prior to treatment.

For diary data, baseline values will be the average of all diary data from the screening period (Days -14 through -1, inclusive, relative to day of first dose). If more than 14 days of diary data are collected during the screening period only the data from Day -14 onwards will be used. If fewer than 8 days are available then the baseline value will be set to missing.

Centers may be pooled geographically if necessary for analysis purposes. This will be determined before database lock.

CROSS-REGIONAL TEMPLATE

Template Number: C-TMPL-DO-801

Page: 17 of 28

Version Number: 1.2

Effective Date: 14 Sep 2015

This version replaces: 1.1

Parent Document: C-SOP-DO-800

Template Title: Statistical Analysis Plan (Legacy Takeda)

For weekly SBM frequency, at least 4 days of diary data are required to compute a weekly estimate, if there are less than 4 days recorded in a week then the SBM frequency for that week will be set to missing.

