7.8.1 Primary Efficacy Endpoint(s)

The primary efficacy endpoint is SBM frequency at Week 1; an SBM is defined as any BM that does not occur within 24 hours after rescue medication use. Since rescue medication use will be disallowed during Week 1, the SBM frequency should equal the BM frequency. In the case of protocol violators, the analysis will be based on SBMs.

In order to adjust for early withdrawals or those with less than 7 days diary data, weekly SBM frequency will be calculated as follows:

$$7 \times (\text{Number of SBMs} / \text{Number of days}),$$

where the number of days is the number of days during the week that the subject was in the study. Weeks will be calculated as 168-hour intervals starting from the day after randomization (Day1), if there is no time recorded for the morning dose on Day1 then the time of the first recorded morning dose will be used. The number of days will generally be 7 unless a subject drops out during a treatment week. If the number of days is less than 4, then the data will be considered insufficient and the frequency will be missing.

Primary Analysis

Since outliers are commonly observed in these data, parametric models may not be robust. The efficacy data will therefore be analyzed by a van Elteren test stratified by center. If necessary, small centers will be pooled as mentioned above. This procedure will test the null hypothesis of equal SBM rates between treatments at the end of Week 1 versus the alternative hypothesis of non-equality between the 2 groups; the test will be conducted at a 2-sided significance level of 0.05. A related 95% confidence interval and point estimate will be provided for the treatment difference; the confidence interval will be estimated by inverting the hypothesis test. This endpoint will be analyzed for the FAS.

Sensitivity Analyses

The primary analysis as described above will be repeated using the PP rather than the FAS. An additional sensitivity analysis using the FAS assuming a ‘worse-case’ scenario approach will also be conducted, where missing values, including those with < 4 days diary data, are assigned the worst case values (the lowest SBM frequency for week 1) recorded in the study by any subject for that endpoint at that time.

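### SAP 7.1 applies the significance label to p-values after rounding to three decimals, a nominal cutoff of p < 0.0505, slightly looser than the stated two-sided 0.05 level

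*SAP*

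**What the plan says.** SAP 7.1 (General Principles) opens its rules on testing with "All confidence intervals, statistical tests, and resulting p-values will be reported as 2-sided unless otherwise stated". The next sentence sets the labelling rule: "P-values (when rounded to three decimals) less than or equal to" alpha, given as 0.05, are to be described as statistically significant. The rule is general and makes no exception for the primary test.

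The level of the tests is stated elsewhere:

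- SAP 7.8 (Efficacy Analysis): "Two-sided tests at a significance level of" 5% are used throughout unless otherwise stated. Protocol 13.1.3 says the same. SAP 7.8 adds: "There will be no adjustment for multiplicity".
- SAP 7.8.1, on the primary van Elteren test: "the test will be conducted at a 2-sided significance level of 0.05". A 95% confidence interval accompanies it, and "the confidence interval will be estimated by inverting the hypothesis test".
- SAP 6.0 and protocol 13.3 also size the trial at a two-sided 0.05.

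The protocol has no rounding rule. SAP 7.13 says only that the SAP adds detail and further analyses; it does not declare a changed threshold. Neither document says whether the rounded or the unrounded p-value governs.

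**The concern.** Rounding a p-value for a table is harmless. Rounding it before comparing it with alpha moves the cutoff. A p of 0.0504 is above 0.05, so the test in SAP 7.8.1 does not reject; under SAP 7.1 it becomes 0.050 and is called significant.

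The shift goes one way only. No p at or below 0.05 loses the label, and every p whose label changes moves from non-significant to significant.

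What is at stake is the wording of the conclusion in a narrow borderline band. There the report could call the primary result significant beside a 95% interval, built from the same test, that includes no difference. SAP 7.8.2 uses the same interval construction for straining and abdominal symptoms (and stool consistency by reference to straining), so the mismatch could also appear there.

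**Working it through.** **Inputs.** The labelling rule is from SAP 7.1 and the two-sided level of 0.05 from SAP 7.8 and 7.8.1 and protocol 13.1.3. The design figures are from SAP 6.0: "Assuming equal allocation, a power of 90%, an alpha level of 0.05 for a 2-sided test, a placebo mean of 4", and "a treatment mean of 5.9 and a common standard deviation of 4 for SBM frequency at Week 1". The difference is 5.9 − 4 = 1.9, and the stated total is 198.

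**1. The plan's own sample size at alpha 0.05.**

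- Normal formula, per arm: 2 × [SD × (z for 1 − α/2 + z for power) / difference]² = 2 × [4 × (1.9600 + 1.2816) / 1.9]² = 93.14.
- Multiplied by π/3, the Wilcoxon factor under normality: 97.54, rounded up to 98 per arm, 196 in total.
- Noether's formula: P(active > placebo) = Φ(1.9 / (4√2)) = 0.6315, so N = (1.9600 + 1.2816)² / [12 × 0.25 × (0.6315 − 0.5)²] = 202.5, rounded up to 203.

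The two approximations bracket the stated 198, so the design is consistent with a two-sided 0.05.

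**2. The cutoff implied by SAP 7.1.** With ordinary half-up rounding:

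| p | rounded to 3 decimals | label under SAP 7.1 | p ≤ 0.05 unrounded? |
|---|---|---|---|
| 0.0499 | 0.050 | significant | yes |
| 0.0500 | 0.050 | significant | yes |
| 0.0503 | 0.050 | significant | no |
| 0.05049 | 0.050 | significant | no |
| 0.0505 | 0.051 | not significant | no |

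The rule is equivalent to p < 0.0505.

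**3. Nominal level.** For a continuous p-value that is uniform under the null, the chance of receiving the label is 0.0505. The excess is 0.0505 − 0.0500 = 0.0005, and 0.0005 / 0.05 = 1%. The critical |z| falls from 1.9600 to 1.9557. In 20 million simulated uniform p-values the rates were 0.0506 with rounding and 0.0501 without, a difference of 0.0005.

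**4. Effect on the design.** With the Wilcoxon factor, the total before rounding up is 195.1 at 0.05 and 194.6 at 0.0505; both round up to 98 per arm. Power at 99 per arm is 90.4% and 90.5%.

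**5. How often the label would change.** The chance that p falls between 0.0500 and 0.0505 is 0.05% under the null. Under the planned alternative it is about 0.07% (normal approximation), the difference between the two unrounded powers in step 4 (0.9049 − 0.9042 = 0.0007). Either way it is well under 1 trial in 1,000.

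**6. Agreement with the interval.** A 95% interval from inverting a test excludes no difference when that test rejects at 0.05. The interval matching a cutoff of 0.0505 would have level 1 − 0.0505 = 94.95%. Between the two cutoffs, the label and the planned 95% interval would generally disagree.

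**The case against.** The strongest reply is that SAP 7.1 is a presentation rule. It sits beside the decimal-place conventions, it names 0.05 as alpha, and it governs what is reported as significant. SAP 7.8.1 is specific to the primary endpoint and says that the test is conducted at 0.05. On that reading the specific text governs the test and the general text only the label.

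Much of this stands. A reader might infer from SAP 7.1 that the confirmatory test is not run at 5% at all. The documents do not support that: every statement about the test itself gives 0.05, and no order of precedence puts SAP 7.1 above SAP 7.8.1. A reader might also infer that the realised type I error is 0.0505. That does not follow either. The 0.0505 is a nominal figure for a continuous p-value; the endpoint is a tied weekly count, and the van Elteren p-value is taken here to be the usual asymptotic one. Its true size will differ slightly from nominal under any rounding rule and was not computed.

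Ties also limit the argument about the interval. An interval from inverting a rank test on tied data can end exactly at zero, so agreement at the boundary is not guaranteed even with unrounded p-values.

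The reply does not remove the point. SAP 7.1 is the only explicit rule for attaching the word significant to a result, it has no exception for the primary test, and nothing says that rounding is for display. Prespecification does not settle the matter, because the label and the test level are both prespecified and differ.

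**Conclusion.** The point holds as a minor inconsistency. The labelling rule in SAP 7.1 implies a nominal cutoff of p < 0.0505, while the tests are specified at a two-sided 0.05. The nominal excess is 0.0005 per test, the sample size is unchanged, and power moves by less than 0.1 percentage point. What remains is a narrow band in which the report could call the primary result significant against its own test and, in general, its own interval.

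This assumes half-up rounding and, for the level, a continuous null p-value; the figures under the alternative use a normal approximation with the design values in SAP 6.0. The less-than-or-equal sign is not a fault, since p ≤ 0.05 on the unrounded value is a valid rule at level 0.05. The fault is only in rounding first. For the secondary endpoints, which have no multiplicity adjustment, a shift of this size has little inferential meaning.

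**What to change.** In SAP 7.1, replace the rounding rule with a sentence to this effect: statistical significance is judged on the unrounded p-value (p ≤ 0.05), and p-values are rounded to three decimals for display only. Keep the existing less-than-or-equal sign.

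The cost is one sentence. No data collection, analysis method, sample size or protocol text changes. It should be made before unblinding, so that the threshold cannot appear to have been chosen around a borderline result.
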